Study title: Could Apnea Induce Hypoalgesia? An Explorative Randomized Controlled Trial.

Date uploaded: 27/02/2023.

Statistical analysis.

Shapiro-Wilks test was employed to examine normal data distribution between groups for all variables. According to its results, T-test for independent samples or Mann-Whitney U tests were employed to examine differences between groups in baseline data.

Repeated measures ANOVA was employed to test time, group and time x group interaction effects on pressure pain threshold (PPT) for the dorsal distal-phalange base of the thumb dominant arm and tibialis anterior muscle belly of the dominant leg, respectively.

Repeated measures ANOVA was also employed for evaluating conditioned pain modulation (CPM) responses for upper limbs, analysing basal and conditioned PPT before and after interventions. Time, group, and time x group interaction effects were explored.

Arterial oxygen saturation, and heart rate (HR) response were explored with a repeated measures ANOVA, with the basal and during-training values between groups, for mean partial oxygen saturation (SpO_2), minimum SpO_2 , mean $\%HR_{max}$, and peak $\%HR_{max}$ were explored. Times through the 4 hypoxemia zones and 5 $\%HR_{max}$ zones were explored for pairwise differences between groups with T-Student test for independent samples or Mann-Whitney U test.

According to normal distribution analysis, Spearman rank or Pearson tests were used to evaluate linear correlations between PPT post-preintervention changes and the following variables: (1) basal CPM response (difference between conditioned and unconditioned pre-intervention PPT); (2) rated perceived exertion (RPE); (3) mean SpO_2 , minimum SpO_2 value, and time in the 4 hypoxemia zones; (4) mean $\%HR_{max}$, peak $\%HR_{max}$, and time in the 5 zones of $\%HR_{max}$. All these correlation analyses were explored only in the apnoea group. As a secondary objective we aimed to establish associations between RPE and HR and SpO_2 in the apnoea group.

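### PPT at each site is analysed by repeated measures ANOVA without a baseline covariate; ANCOVA on pre-intervention PPT would usually be more precise and costs at most 1/(N−4) in variance

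*SAP*

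**What the plan says.** The second paragraph of the Statistical analysis section covers the main pain outcome: "Repeated measures ANOVA was employed to test time, group and time x group interaction effects on pressure pain threshold (PPT"). The model is applied separately at the "dorsal distal-phalange base of the thumb dominant arm and tibialis anterior muscle belly of the dominant leg, respectively". Pre-intervention PPT enters only as one of the repeated outcomes. No baseline covariate and no ANCOVA appears anywhere in the SAP, and the paragraph does not say which of the three effects is the test of apnoea.

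That paragraph lists no measurement times. A pre/post structure is implied elsewhere: the correlation paragraph uses "linear correlations between PPT post-preintervention changes and the following variables", and the CPM paragraph describes "analysing basal and conditioned PPT before and after interventions". The correlation paragraph also shows that a pre-intervention PPT value is collected, since it defines the "basal CPM response (difference between conditioned and unconditioned pre-intervention PPT").

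**The concern.** With two groups and one value before and one after, the time x group F statistic equals the square of the t statistic comparing mean change between groups. A change score subtracts the whole baseline, so it assumes that one unit of pre-intervention PPT predicts exactly one unit of post-intervention PPT. When measurements vary between occasions the true slope is often below 1. Subtracting the whole baseline then adds noise that an estimated slope would avoid.

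The PPT comparison is the one that bears on the title question. A narrower interval for the between-group difference could be had from data already collected, without more participants. What is at stake is precision only: the planned test is unbiased, and the trial describes itself as "An Explorative Randomized Controlled Trial".

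**Working it through.** **The plan's own figures.** The SAP states no sample size, SD, pre-post correlation, allocation ratio, alpha or power, so there is no figure to reproduce.

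**From the SAP.** The trial is randomised. There are two groups, inferred from the two-sample tests used at baseline. Each site has pre and post PPT values, inferred as described above.

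**Assumed.** One pre and one post value per site; 1:1 allocation with n per arm and N = 2n; the same covariance matrix in both arms; roughly normal data; N of 20 or 40; pre-post correlation ρ from 0.5 to 0.9; ratio k = post SD / pre SD of 0.8, 1 or 1.25. For power only: a true effect of 0.5 pre-intervention SD and two-sided alpha 0.05.

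**Step 1. Equivalence.** In a numerical example with 10 per arm, the time x group F and the squared t for change were both 2.9506.

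**Step 2. Variances of the group difference**, in units of (pre SD)² × 2/n:

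- Change score: k² + 1 − 2ρk
- ANCOVA: k²(1 − ρ²) × [1 + 1/(N − 4)], where the bracket is the expected cost of estimating the slope

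With the true slope b = kρ, the change variance can be written k²(1 − ρ²) + (1 − b)². In large samples ANCOVA is therefore never less precise, and the two are equal only at b = 1.

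**Step 3. Worst case.** At b = 1 the ratio ANCOVA/change is 1 + 1/(N − 4): 37/36 = 1.028 at N = 40 and 17/16 = 1.0625 at N = 20. ANCOVA also gives up one degree of freedom. Counting that in the t quantile, the squared CI width is at worst 3.0% (N = 40) or 7.2% (N = 20) larger.

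**Step 4. Variance ratios, ANCOVA / change score** (below 1 favours ANCOVA). Example for N = 40, k = 1, ρ = 0.7: (1 − 0.49) × 37/36 = 0.524; 2 − 1.4 = 0.6; ratio 0.874.

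| N | k | ρ = 0.5 | 0.7 | 0.8 | 0.9 |
|---|---|---|---|---|---|
| 40 | 0.8 | 0.587 | 0.645 | 0.658 | 0.625 |
| 40 | 1 | 0.771 | 0.874 | 0.925 | 0.976 |
| 40 | 1.25 | 0.918 | 1.008 | 1.028 | 0.976 |
| 20 | 0.8 | 0.607 | 0.667 | 0.680 | 0.646 |
| 20 | 1 | 0.797 | 0.903 | 0.956 | 1.009 |
| 20 | 1.25 | 0.949 | 1.042 | 1.063 | 1.009 |

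With k = 1 the ratio is (1 + ρ)/2 × (N − 3)/(N − 4). ANCOVA therefore has the smaller variance for ρ below (N − 5)/(N − 3), which is 35/37 = 0.946 at N = 40 and 15/17 = 0.882 at N = 20.

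**Step 5. Power at N = 40**, time x group / ANCOVA, in %, from the noncentral t with N − 2 and N − 3 degrees of freedom:

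| k | ρ = 0.5 | 0.7 | 0.8 | 0.9 |
|---|---|---|---|---|
| 0.8 | 39/59 | 57/76 | 73/89 | 93/99 |
| 1 | 34/42 | 51/57 | 68/72 | 93/94 |
| 1.25 | 27/29 | 40/40 | 54/53 | 79/80 |

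Over this grid the difference runs from a gain of about 20 points (39.0% to 59.2%) to a loss of about 1 point (53.8% to 52.6%). At N = 20 the loss in the worst cell (k = 1.25, ρ = 0.8) is 1.6 points (29.2% to 27.6%).

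**Step 6. Simulation.** With 200,000 replicates per setting, the simulated ratios at k = 1 were within about 0.003 of the formula, and the worst cases came out at 1.029 (N = 40) and 1.063 (N = 20). In a separate run of 40,000 trials per cell, both methods had a mean estimate of 0.50 in every cell. Type I error at k = 1, ρ = 0.7 was 4.9% (change) and 5.0% (ANCOVA) at N = 40, and 5.0% and 5.1% at N = 20.

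**The case against.** The strongest reply is that this is a choice between two acceptable methods. The time x group test is valid, standard and already uses the baseline, and nothing in the SAP contradicts it. That stands, and it is why the point is a suggestion and not a correction.

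The size of the gain is also unknown. The 20-point gain in power needs a post-intervention SD 20% below baseline, which nothing in the SAP suggests. With equal SDs and N = 40 the gain is about 8 points at ρ = 0.5, 5 at 0.7, 3 at 0.8 and under 1 at 0.9. ANCOVA is less precise in 2 of the 12 cells at N = 40 and in 4 of 12 at N = 20. This stands too: the word usually describes an assumed range, not data from this trial. What does not depend on ρ or k is the ceiling on the loss, 1/(N − 4), so the trade is lopsided in ANCOVA's favour.

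Two further objections stand as limits. The single post-intervention value is inferred, and with several post values the figures would not apply as written. The SAP is in the past tense, so the analysis may already have been run; replacing a stated test after seeing the data adds analytic flexibility, which is why the post hoc label is needed.

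**Conclusion.** The concern holds as a low-stakes efficiency point. The planned PPT analysis is unbiased but fixes the baseline slope at 1. Adjusting for pre-intervention PPT would give a more precise comparison over most of the plausible range, with a small, bounded downside. Confidence is medium, because the benefit depends on a sample size, SDs and a correlation that the SAP does not give, and on the assumed 1:1 allocation and single pre and post values.

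That the SAP does not name time x group as the test of apnoea is a matter of wording. It is worth settling, because the group main effect averages pre and post values and so targets only half of a post-intervention difference.

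**What to change.** For each PPT site, estimate the between-group difference in post-intervention PPT by ANCOVA, with group and that site's pre-intervention PPT in the model. Report it with a 95% CI as the test of apnoea at that site, and treat the time and group main effects as descriptive. If data have already been seen, label the model post hoc.

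If the repeated measures ANOVA is kept, name time x group as the test of apnoea and report the between-group difference in change with a 95% CI. How the two sites rank is left to the protocol.

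The cost is a change of SAP wording and one model line per site. No new data are needed. The statistical price is one degree of freedom and the bounded loss of variance shown in Step 3.

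### The CPM ANOVA names basal and conditioned PPT as its data but lists only time, group and time x group; fitted to those raw values, no listed term isolates a change in CPM

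*SAP*

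**What the plan says.** The unnumbered CPM paragraph of the SAP's Statistical analysis section gives the following:

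- **Purpose:** "Repeated measures ANOVA was also employed for evaluating conditioned pain modulation (CPM) responses for upper limbs".
- **Data and terms:** "analysing basal and conditioned PPT before and after interventions. Time, group, and time x group interaction effects were explored".

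The only definition of a CPM response is in the later correlation paragraph, "basal CPM response (difference between conditioned and unconditioned pre-intervention PPT". It covers the pre-intervention value, which is used as a correlate of PPT change in the apnoea group. The CPM paragraph neither refers to it nor extends it to the post-intervention value.

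**The concern.** The data named form a 2 x 2 layout within each participant: basal or conditioned, by before or after. The listed terms contain one within-person factor, time. Two readings are open.

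1. The outcome is the CPM response, conditioned minus basal PPT, at each time point. The listed terms are then complete, and time x group tests whether CPM changed differently between groups.
2. The model is fitted to the raw PPT values that the sentence names. The effect on CPM is then the conditioning x time x group interaction, which is not listed.

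The stakes are specific to this trial. Its title asks whether apnoea induces hypoalgesia, that is, a general rise in PPT. Under reading 2 such a rise produces a time x group effect in an analysis labelled CPM even if CPM has not moved. The result would partly repeat the PPT analysis of the preceding paragraph under another name.

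**Working it through.** The SAP states no figure on this point to reproduce. The core is algebra and needs no assumed values.

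**Contrasts.** Order the cells pre-basal, pre-conditioned, post-basal, post-conditioned.

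- Pre/post time, averaged over conditioning: (-0.5, -0.5, +0.5, +0.5).
- Change in CPM: (+1, -1, -1, +1).
- Dot product: -0.5 + 0.5 - 0.5 + 0.5 = 0. The two contrasts are orthogonal.

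With b and c the between-group differences in pre-to-post change of basal and conditioned PPT:

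- two-level time x group on raw PPT estimates (b+c)/2;
- the CPM effect (conditioning x time x group, or equivalently time x group on the difference score) is c-b.

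**What follows directly.**

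- Both rise by d (b = c = d): raw time x group is d, the CPM effect is 0.
- Only basal PPT rises by d: raw time x group is +d/2, while CPM falls by d. The sign is wrong.
- Basal falls and conditioned rises by the same amount: raw time x group is 0 although CPM rises.

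**Other ways to fit raw values.** A four-level time factor gives a 3-df test that contains the CPM contrast but mixes it with PPT change. Separate ANOVAs for basal and conditioned PPT estimate b and c, each a PPT change. Separate pre and post ANOVAs, with basal/conditioned in the role of time, compare CPM at one occasion rather than its change. None isolates a change in CPM.

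**Illustrative rates, reading 2 only.** The SAP gives no sample size, SD or effect size, so all inputs are assumed: independent within-person errors with SD s, n per arm, two-sided 5%.

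- Two-level: effect (b+c)/2, SE s√(2/n), 2n-2 df.
- Three-way: effect c-b, SE 2s√(2/n), 2n-2 df.
- Four-level: F on 3 and 3(2n-2) df, noncentrality 2n·Σ(centred profile/2)²/s², the profile being (0, 0, b, c).

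At n = 20 and s = 0.5 the SEs are 0.5√(2/20) = 0.158 and 2 × 0.158 = 0.316. For b = c = 0.4 the two-level ratio is 0.4/0.158 = 2.53 and the three-way ratio is 0. The centred profile is (-0.2, -0.2, 0.2, 0.2), so the noncentrality is 40 × 4 × 0.01/0.25 = 6.4. Exact noncentral t and F give:

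| b, c (n = 20, s = 0.5) | Two-level | Four-level | Three-way |
|---|---|---|---|
| 0.4, 0.4 | 69.3% | 53.2% | 5.0% |
| 0, 0.6 | 45.6% | 78.1% | 45.6% |
| 0.6, 0 | 45.6% (estimate +0.3) | 78.1% | 45.6% (estimate -0.6) |
| -0.3, 0.3 | 5.0% | 58.7% | 45.6% |

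Simulation with 6,000 runs per row agrees to within about one percentage point. Over n = 15 to 30 per arm (two-level / four-level / three-way):

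- common rise 0.2: 18-33% / 13-22% / 5%;
- common rise 0.4: 56-86% / 41-73% / 5%;
- one threshold only rises 0.6: 36-63% / 64-93% / 36-63%.

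Only the ratio of effect to s matters, so a rise of 0.4 with s = 1 gives the same rates as 0.2 with s = 0.5.

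**ANCOVA.** Take equal pre and post variance σ² of the CPM difference and pre-post correlation ρ. Per-person variance is σ²(1-ρ²) for ANCOVA and 2σ²(1-ρ) for the change score, a ratio of (1+ρ)/2: 0.50 at ρ = 0, 0.75 at 0.5 and 0.95 at 0.9. With the change-score ratio of effect to SE held at 1.90 (n = 20), power is about 74%, 57% and 47.5%, against 46% for the change score. The values of ρ are a separate assumption; under the independent-error model above ρ is 0.

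**The case against.** The strongest reply is that the benign reading is the natural one. The stated object is CPM responses, the SAP's only definition of such a response is a difference, and with a difference score the three listed terms are exactly the full set. The raw values may be named only as ingredients. This stands as a plausible reading, and the SAP is no proof that a wrong model was fitted.

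It does not settle the matter. The next paragraph speaks of a response and then names raw values as what enters the model: "heart rate (HR) response were explored with a repeated measures ANOVA, with the basal and during-training values between groups". That parallel is limited, because there the basal and during-training values are themselves the levels of time, but it shows that the word alone does not imply a difference. Where the SAP means a difference elsewhere it says so, as in "linear correlations between PPT post-preintervention changes".

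A second reply is that outcome derivation may sit in a protocol that is not shown. Here, however, the SAP itself states data and terms, and together they do not determine one test.

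Third, the trial is exploratory, the harm depends on reading 2 and on the pattern of PPT change, and the rates rest on assumed inputs. This is fair for the rates, and the missed-effect case needs exactly opposite shifts. It does not affect the algebra, and the common-rise case is the one the title asks about.

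Finally, ANCOVA is not needed to cure the ambiguity. That is correct; it is offered as a gain in precision.

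**Conclusion.** The concern holds in its conditional form. The SAP leaves open which contrast its CPM ANOVA tests. If the outcome is conditioned minus basal PPT, the plan is sound and no result changes. If the raw values are modelled as the sentence literally says, two-level time x group targets (b+c)/2 instead of c-b and can report hypoalgesia as a CPM effect or give the wrong sign; the four-level version cannot separate the two. This conclusion rests on algebra alone. How often it would mislead cannot be known from the SAP; the percentages only show that the error need not be small. It should be fixed, with medium confidence, because the wording does not show which model was meant.

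**What to change.** - State that the CPM outcome is conditioned minus basal PPT, computed at each time point, and that the CPM test is time x group on that difference. This is identical to conditioning x time x group in a 2 x 2 x 2 model.
- Preferably, compare post-intervention CPM between groups by ANCOVA adjusted for pre-intervention CPM. Under randomisation it estimates the same effect, usually more precisely, from values already collected.
- State that time, group and time x group effects on raw PPT are not interpreted as CPM results.

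If the difference score was the outcome, the cost is one clarifying sentence. If raw PPT was modelled, it is one re-specified model on existing data, with any CPM conclusion drawn from the raw-PPT terms revisited.

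### PPT change is correlated with 15 overlapping predictors in one arm with no multiplicity handling, and the CPM correlation may be partly built in

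*SAP*

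**What the plan says.** The last paragraph of the SAP's Statistical analysis section sets out the correlations: "Spearman rank or Pearson tests were used to evaluate linear correlations between PPT post-preintervention changes and the following variables". Four numbered groups follow:

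- Group 1 is "basal CPM response (difference between conditioned and unconditioned pre-intervention PPT".
- Group 2 is rated perceived exertion.
- Group 3 is "mean SpO_2 , minimum SpO_2 value, and time in the 4 hypoxemia zones".
- Group 4 is mean and peak %HRmax and the time in each of five %HRmax zones.

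The paragraph adds: "All these correlation analyses were explored only in the apnoea group". It closes with a further set: "As a secondary objective we aimed to establish associations between RPE and HR and SpO_2 in the apnoea group".

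Earlier in the section, the ANOVA is planned for "pressure pain threshold (PPT) for the dorsal distal-phalange base of the thumb dominant arm and tibialis anterior muscle belly of the dominant leg", so PPT is measured at two sites. The correlation paragraph does not say whether one or both are used. The SAP gives no significance level, no multiplicity procedure and no ranking of the correlations. The title describes the study as "An Explorative Randomized Controlled Trial".

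**The concern.** Two separate problems arise in the same paragraph.

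The first is the number of tests. Many correlations are tested against one outcome in one arm, so some nominally significant results are likely even if nothing is related to PPT change. Thirteen of the 15 predictors summarise either the SpO2 recording or the heart-rate recording. Two or three significant results in one of these blocks may therefore be one chance finding seen several times, yet look like mutual support.

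The second is coupling. Basal CPM subtracts an unconditioned pre-intervention PPT, and PPT change also subtracts a pre-intervention PPT. If it is the same reading, its measurement error enters both variables with the same sign and produces a positive correlation. That is the direction a reader would take to mean that people with stronger pain modulation gain more from apnoea. No multiplicity adjustment removes it.

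**Working it through.** The SAP gives no figure to reproduce.

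**Inputs from the SAP.** Predictors: 1 (CPM) + 1 (RPE) + 6 (SpO2: mean, minimum, 4 zones) + 7 (heart rate: mean, peak, 5 zones) = 15. PPT sites measured: 2, so 15 × 2 = 30 tests if both are used.

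**Assumed, because the SAP does not state them.** Two-sided 5% level, no true associations, and 15 to 30 apnoea participants in the simulations.

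**Expected chance findings** (m × alpha, whatever the overlap):
- 15 × 0.05 = 0.75
- 30 × 0.05 = 1.5
- At a 1% level: 15 × 0.01 = 0.15 and 30 × 0.01 = 0.30

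**Chance of at least one, if the tests were independent:**
- 1 − 0.95^15 = 0.537
- 1 − 0.95^30 = 0.785

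**Effect of overlap.** Overlap leaves the expected count unchanged but lowers the chance of any finding. The null simulation used 4,000 runs with n = 15 and 25. Correlation among metrics of the same recording ran from 0.3 to 0.9, and the two sites were correlated at 0.5.
- 15 tests: about 51% down to 28%
- 30 tests: about 73% down to 45%

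Other simulations with similar assumptions gave 30-52% and 32-53% for 15 tests. With the independent case as the upper end, roughly 30-54% is a fair range. A narrower one would reflect the chosen model of the recordings, since the SAP does not fix how strongly the metrics are related.

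**Effect of Benjamini-Hochberg over the 15 tests.** With all nulls true and CPM not coupled to the outcome, the chance of any association passing falls to about 4-6%.

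**RPE family.** If all 6 + 7 = 13 SpO2 and heart-rate metrics were used, 13 × 0.05 = 0.65 chance findings would be expected. The SAP names only HR and SpO2 here, so the number may be smaller.

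**Coupling of CPM and PPT change.** Suppose each PPT reading has independent error variance s², and each difference also has true individual variance v·s², with no real link between the two.
- CPM = conditioned − baseline; change = post − baseline.
- Covariance from the shared baseline error: s².
- Variance of each difference: 2s² + v·s².
- Null correlation: s² / (2s² + v·s²) = 1/(2 + v).

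| v | Null correlation | CPM passes Benjamini-Hochberg (simulated, n = 15 to 30) |
|---|---|---|
| 0 | 1/2 = 0.50 | 12-40% |
| 1 | 1/3 = 0.33 | 4-11% |
| 4 | 1/6 = 0.17 | about 1-2% |

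The size therefore depends on v, which the SAP does not give.

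**The case against.** The strongest reply is that the study is explorative by title and that the SAP says these correlations were explored. A broad search is legitimate in such a study, and formal family-wise control is not obligatory. This stands, and it is why the point is minor.

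It is also fair that the SAP names every predictor, so the expected number of chance findings is simply m × alpha. A reader might infer that this number cannot be known. The document does not support that: only the missing significance level and PPT site(s) stand in the way, and one sentence would supply them. The SAP also already groups the SpO2 and heart-rate variables, so their common source is visible.

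Adjusted p-values say nothing about clustering, because near-duplicate metrics can pass together. That is correct, so the blocks need their own treatment in the report. Nor would passing the adjusted level make a one-arm correlation more than hypothesis-generating.

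On CPM, the SAP does not say that the baseline reading is shared. It places CPM at the upper limbs and one PPT site at the thumb, which makes sharing the natural reading for that site but not a certainty.

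What remains is that an explorative label does not by itself tell readers how many tests were run, what chance would yield, or that one correlation may be partly arithmetic.

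**Conclusion.** The point holds as a low-severity matter of reporting and interpretation. The plan tests 15 overlapping predictors of PPT change in the apnoea group, or 30 correlations if both sites are used, without any multiplicity handling. At an assumed two-sided 5% and with no real associations, 0.75 or 1.5 chance findings are expected. The chance of at least one among 15 is roughly 30-54%, and about 4-6% after Benjamini-Hochberg.

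The coupling of CPM with PPT change is conditional on a shared baseline reading. If it is shared, the null correlation is 1/(2 + v), illustrated by 0.50, 0.33 and 0.17 for v = 0, 1 and 4. These values are not bounds on what the trial would show.

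Three stronger inferences are not supported. The overlap does not raise the expected number of false findings. The SAP does not commit to 30 tests. Nothing here touches the between-group ANOVAs, which do not use these correlations.

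**What to change.** In the SAP, or in the report if analysis is complete:

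- State the significance level, the PPT site(s) used for the correlations, and the number of tests in each family (PPT change; RPE).
- Report Benjamini-Hochberg adjusted values within each family and a 95% confidence interval for each correlation, beside the raw p-values.
- Describe all these correlations as hypothesis-generating, whether or not they pass the adjusted level.
- Present the SpO2 metrics as one block and the heart-rate metrics as another, each from a single recording, and do not count several results within a block as independent support.
- State whether basal CPM and upper-limb PPT change use the same baseline reading. If so, flag that correlation as partly built in and do not interpret it as evidence of a link. The correlation of CPM with tibialis anterior PPT change does not share that reading and can be shown beside it.

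The cost is some wording, one added column and the intervals, all from existing data. The downside is that fewer associations pass the adjusted level. For a simulated true correlation of 0.57 between mean SpO2 and PPT change (one site, 15 tests), the share passing falls from 52% to 25% at n = 15, from 66% to 39% at n = 20 and from 84% to 62% at n = 30. The raw p-values should therefore stay visible.

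### Thumb PPT change and basal CPM appear to share one baseline reading; if so, testing their correlation against zero in the apnoea group has the wrong null

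*SAP*

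**What the plan says.** The correlation paragraph of the SAP (Statistical analysis) sets out "linear correlations between PPT post-preintervention changes and the following variables: (1) basal CPM response (difference between conditioned and unconditioned pre-intervention PPT". The test is Pearson or Spearman, chosen by the normality results. The paragraph adds: "All these correlation analyses were explored only in the apnoea group".

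Two other paragraphs show which readings are involved:

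- The PPT paragraph names two sites: "dorsal distal-phalange base of the thumb dominant arm and tibialis anterior muscle belly of the dominant leg, respectively".
- The CPM paragraph describes "conditioned pain modulation (CPM) responses for upper limbs, analysing basal and conditioned PPT before and after interventions", and says of that analysis: "Time, group, and time x group interaction effects were explored". CPM readings therefore exist in both arms.

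The SAP does not name the CPM test point. It mentions no second unconditioned pre-intervention reading, and no adjustment for a component common to the two correlated quantities.

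**The concern.** Each correlated quantity is a difference with an unconditioned pre-intervention PPT subtracted. For the thumb, the natural reading is that this is one and the same measurement. A participant whose baseline happened to read low would then show both a larger rise after apnoea and a larger CPM effect, and one whose baseline read high would show the reverse. That alone produces a positive correlation, so zero is not the value expected when CPM and response are unrelated. Choosing between Pearson and Spearman does not help, because both are affected.

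A significant positive result would probably be read as better baseline CPM going with more apnoea-induced hypoalgesia, when shared measurement error could account for it. Restricting the analysis to the apnoea arm also leaves out the control arm, where the same coupling would show.

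The stakes are limited. The trial is exploratory. Basal CPM is one of 15 correlates (CPM 1, RPE 1, SpO2 2 + 4, heart rate 2 + 5) and only one of the two PPT sites is involved. The randomised time-by-group tests are untouched.

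**Working it through.** **Inputs.** From the SAP: the two differences, the sites, the restriction to the apnoea group, and the tests. The SAP gives no figure to reproduce. Assumed: 15–30 participants in the apnoea group, a two-sided 5% test, a shared baseline reading, and the variances below.

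**Model.** For one participant let

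- pre-intervention unconditioned reading U = T + e1
- pre-intervention conditioned reading C = T + A + e2
- post-intervention reading P = T + B + e3

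T is the true threshold, A the true CPM effect (variance vC) and B the true response (variance vR), with A and B unrelated. The error variances are v1, v2 and v3. The errors of U and C share a covariance c, and e3 is independent of both.

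**Covariance.** Change = P − U = B + e3 − e1. Basal CPM = C − U = A + e2 − e1. T cancels from both, leaving Cov = v1 − c. Hence, with no true relationship,

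r = (v1 − c) / √[(vC + v1 + v2 − 2c)(vR + v1 + v3)],

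which is above zero whenever c < v1.

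**Numbers.** Set v2 = v3 = 1 and vC = vR = k. The last column is the false-positive rate of the Pearson test as n goes from 15 to 30 (20,000 simulated trials per setting; mean simulated r within 0.02 of the formula throughout).

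| Baseline error | k | Expected r | False positives |
|---|---|---|---|
| v1 = 1, c = 0 | 1 | 1/3 = 0.33 | 23–44% |
| | 2 | 1/4 = 0.25 | 14–27% |
| | 4 | 1/6 = 0.17 | 9–14% |
| | 8 | 1/10 = 0.10 | 6–8% |
| | 12 | 1/14 = 0.07 | 6–7% |
| v1 = 0.5, c = 0 | 1 | 0.5/2.5 = 0.20 | 11–18% |
| | 4 | 0.5/5.5 = 0.09 | 6–8% |
| | 8 | 0.5/9.5 = 0.05 | 5–6% |
| v1 = 2, c = 0 | 1 | 2/4 = 0.50 | 50–83% |
| | 4 | 2/7 = 0.29 | 18–35% |
| | 8 | 2/11 = 0.18 | 10–16% |
| v1 = 1, c = 0.5 | 1 | 0.5/√6 = 0.20 | 11–19% |
| | 4 | 0.5/√30 = 0.09 | 6–7% |
| | 8 | 0.5/√90 = 0.05 | about 6% |
| v1 = 0.5, c = 0.25 | 1 | 0.25/√5 = 0.11 | 7–9% |
| | 4 | 0.25/√27.5 = 0.05 | 5–6% |

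With equal error variances and c = 0, Spearman gives 21–40% (k = 1), 9–13% (k = 4) and 7–8% (k = 8). The extreme k = 0 gives r = 1/2 and 51–83%, but only as a limit, since nothing then truly varies between participants.

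**Separate readings.** If CPM uses a different unconditioned reading with independent error, the covariance is zero. Simulated rejection was 4.7–5.3% (Pearson) and 4.8–5.4% (Spearman).

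**Interaction across arms.** The slope of change on basal CPM due to coupling is (v1 − c)/(vC + v1 + v2 − 2c). It contains only pre-intervention quantities, so randomisation gives it the same expected value in both arms and it drops out of the slope difference. With no moderation, simulated rejection was 4.8–5.7% and the mean slope difference was within 0.01 of zero. This held when the control arm's response variance equalled that of the apnoea arm and when it was zero.

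**Tibialis anterior.** Leg change and upper-limb CPM share no reading, so this argument does not apply there.

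**The case against.** The strongest objection is that the shared reading is inferred. The SAP speaks of upper limbs in general for CPM, gives no test point, and may leave the number and order of readings to a protocol that is not shown. With separate readings and independent error there is no artefact. This stands as a limit on certainty, and the point is conditional for that reason. It does not remove the point: the SAP itself defines both differences and fixes the test, and its natural reading is a single baseline.

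The size is also undetermined. The table runs from about the nominal 5% to 83%, and the high figures need true variation no larger than single-reading error, or a noisier baseline. That is correct.

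The direction depends on coding. If CPM were taken as unconditioned minus conditioned, the spurious r would be negative. Zero would still be the wrong null.

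Finally, an exploratory analysis might need only a caveat, and the interaction asks something other than the within-apnoea question. The difference in question is real. But an exploratory label does not correct a wrong reference value, and separate readings, where they exist, keep the original question.

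**Conclusion.** The concern holds in conditional form, with medium confidence. If the thumb change and basal CPM use the same unconditioned pre-intervention reading, as the wording implies, a Pearson or Spearman test of r against zero has the wrong null. The inflation depends on the number of participants and on how large true variation is relative to reading error. The document fixes neither, so the effect may be negligible or large. It should be corrected because correction is cheap, but it touches one exploratory correlation and none of the randomised comparisons.

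**What to change.** State which pre-intervention reading enters each difference. Then, for thumb PPT:

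1. Where separate or replicate unconditioned pre-intervention readings exist, use one for the change score and another for the CPM difference. The question stays within the apnoea group.
2. Otherwise, do not test the raw apnoea-only r against zero. Regress thumb PPT change on group, basal CPM and their product in both randomised arms, and test the product term.

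Report the tibialis anterior correlation separately, and label whichever thumb result is given as exploratory.

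The cost is one sentence of SAP wording and one regression on data already analysed in both arms. The drawback of the second option is that it measures moderation relative to control and has low power. As an illustration, suppose the true response rises one unit per unit of CPM, with remaining true response variance k and equal error variances. Power at 15–30 per arm is then:

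| k | Interaction, both arms | Separate readings, apnoea arm |
|---|---|---|
| 1 | 14–26% | 18–35% |
| 4 | 38–70% | 54–85% |
| 8 | 50–83% | 69–95% |

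This is a strong relationship (true correlation √[k/(2k)] = 0.71), and weaker ones would have less power. A non-significant interaction should therefore not be read as absence of a link.
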